3.5.3 Rationale for the Pharmacodynamic Endpoints

The inflammatory pharmacodynamic endpoints of hsCRP and Serum Amyloid A reduction are chosen as they are a direct measures of IL-6 function (specifically their genes are induced by IL-6). Additionally, hsCRP is a clinically relevant measure of inflammation that may be used in future trials. Serum albumin and pre-albumin are also closely negatively correlated with inflammation in the dialysis population as is therefore also being analyzed as a marker of inflammation.

The hematologic pharmacodynamic endpoints chosen are as follows: TSAT, hemoglobin, reticulocyte count, CHr, ESA and iron dose requirements, and erythropoietin resistance index, defined as the epoetin alfa-equivalent dose (weight-based per week in U/kg) divided by the serum hemoglobin (in g/dL). These endpoints are intended to evaluate the effects of reducing inflammation on functional iron deficiency anemia as well as on ESA and iron requirements to maintain hemoglobin at a given (guideline-driven) level. It is hypothesized that CHr will increase as iron is released from tissue stores and that ERI will decrease as hemoglobin rises and/or ESA dose requirements fall assuming administered iron is maintained. The reticulocyte count is expected to transiently increase. TSAT to also expected to increase over time as more iron is mobilized, until iron is utilized for erythropoiesis (reflected in rising hemoglobin), assuming ESA and iron doses remain stable.

Supportive cardiovascular pharmacodynamic endpoints include serum biomarkers (Troponin and NT-proBNP) and left ventricular mass index via MRI. These are chosen based on the documented detrimental effects of IL-6, and beneficial effects of anti-IL-6 therapies, on cardiac structure and function in inflammatory conditions.

Finally, inflammation is known to affect systemic symptoms, notably fatigue and skeletal muscle strength.

3.5.4 Rationale for the Dose Regimens

The main goal of COR-001 dosing in the planned Phase 1/2 hemodialysis patient study is to attain and maintain serum COR-001 concentrations sufficient for $\geq 90\%$ IL-6 binding over the 3-month Treatment Period, with a secondary goal of reducing hsCRP to below 5 mg/L while keeping the highest planned dose more than 20-fold below the no adverse effect level (NOAEL) observed in primates.

Effects on IL-6 and hsCRP

Pharmacokinetic and PD models were created based on data from the Phase 1 trial in RA patients (Study D4430C00001) and used to simulate dosing regimens that achieve the above goals (Section 3.5.4). Based on these models, lower doses were needed to maintain serum COR-001 concentrations above the target value (i.e., that value required to achieve $> 90\%$ IL-6 binding) compared to those needed to normalize hsCRP (defined as $\text{hsCRP} < 5\text{mg/L}$) in a hypothetical hemodialysis population whose baseline hsCRP is at median and serum IL-6 level is above the median. hsCRP normalization in at least 1/3 patients is predicted for cumulative COR-001 dose of ≥ 12 mg, and is not predicted for all patients until cumulative doses of 60 mg or greater are achieved. The COR-001 dose regimens planned are itemized below. Lower doses (including previously studied doses) may be substituted for the planned doses in the table below based on accruing data. In addition, PK and PD results will be reviewed to assess the appropriateness of the next planned dose and to guide revision of the next dose to be evaluated, if necessary.

Dose Cohort	Dose Regimen	Number of Doses	Total Cumulative Dose
1	2 mg every 14 days	6	12 mg
2	6 mg every 14 days	6	36 mg
3	20 mg every 14 days	6	120 mg
4	60 mg every 14 days	6	360 mg

The planned doses all provide plasma IL-6 binding in excess of 90% for the duration of the study, while hsCRP normalization is expected to be attained in 1/3 of patients at the lowest dose, and in 3/3 patients at the highest dose. Full suppression of hsCRP is not believed to be required for beneficial effect on hematologic or iron parameters given the linear correlation between CRP and the degree of erythropoietic inefficiency (Bárány 1997).

As of Amendment 3, the actual doses (all given every 14 days) were 2 mg (Cohorts 1 and 4); 6 mg (Cohorts 2 and 3); 20 mg (Cohort 5).

Safety Margins

The predicted maximum serum COR-001 concentration within a dosing interval (C_{max}), minimum serum COR-001 concentration within a dosing interval (C_{min}), and the cumulative area under the curve from time 0 to infinite time ($AUC_{0-\infty}$) for the planned doses in this study are summarized in Table 1. Table 1 also provides the exposures obtained for the highest dose in the cynomolgus monkey repeat-dose toxicology study (Study 20004916). The exposures for all cohorts in this study have safety margins of ≥ 20 -fold (based on AUC), relative to the no observed adverse effect level (NOAEL) exposures in cynomolgus monkeys.

Table 1 Exposures for Planned Doses and Safety Margins Relative to Toxicology Study

Human						Cynomolgus Monkey
Dosing Schedule		2 mg q14days	6 mg q14days	20 mg q14days	60 mg q14days	100 mg/kg
C_{max} (ng/mL)^a	1st dose	712	2138	7126	21379	2420000
	last dose	1640	4920	16399	49197	3230000
C_{min} (ng/mL)^b	1st dose	268	803	2678	8032	
	last dose	1042	3125	10417	31251	
Cumulative AUC_{0-∞} (ng·day/mL)^c		167447	502372	1674472	5023416	111642743
Safety Margins						
C_{max} (ng/mL)^a	1st dose	3399	1132	340	113	
	last dose	1970	657	197	66	
Cumulative AUC_{0-∞} (ng·day/mL)^c		667	222	67	22	

^a Defined as the mean end of infusion concentration for the simulated subjects.

^b Defined as the mean concentration at the end of the dosing interval for the simulated subjects.

^c Calculated based on the mean clearance for the simulated subjects.

3.6 Safety Plan and Monitoring

The study design, including entry criteria, planned interim safety data reviews, and planned conduct includes a number of elements intended to minimize risk, intended to better monitor for or to mitigate risk to study patients:

- All Study Drug doses will be administered in either a hemodialysis unit or Phase 1 research unit with hemodialysis capabilities in the presence of trained healthcare professionals and resuscitative equipment.
- Patients will be in contact with healthcare professionals three (3) times per week during their hemodialysis treatments, actively observed by study staff for adverse events such as infections, and undergo regular safety monitoring (i.e., vital signs, ECG, physical examination, laboratory evaluations).

- All principal investigators will be nephrologists and therefore skilled in the management of dialysis patients.
- Dose escalation will occur by cohort upon formal safety review as described above. An every-other week dose administration paradigm was chosen based on formal PK/PD modeling to allow for timely withdrawal of investigative therapy if required. The dose escalation decision will also take into account accrued PK/PD data from the study, so that the planned doses can be adjusted, if necessary.
- Dose-Limiting Toxicity criteria and rules for MTD will be pre-defined. Because of the high background frequency of Grade 2 and 3 adverse events in hemodialysis patients (not dissimilar from cancer populations), the DLT threshold will be defined using a threshold of \geq Grade 3 events.
- Initial dosing in each cohort examining a higher dose than studied in a prior cohort will be in two sentinel patients who will be observed for at least 48 hours for early adverse effects before additional patients are dosed.
- Patients will be required to have an absolute neutrophil count of $> 2 \times 10^9/L$ during screening, and decrease in neutrophil count will be treated as a safety event of interest.
- Patients at high risk for infection such as those with temporary hemodialysis catheters, recent or current active infections, smoldering infections, serologic evidence of Hepatitis B or C or HIV, history of tuberculosis (or positive interferon gamma release testing), and baseline neutropenia will be excluded.

Please see the [Guidance to Investigators section](#) of the Investigator's Brochure for a description of safety findings from other IL-6 monoclonal antibodies and guidance for clinical monitoring.

3.7 Benefit and Risk Assessment

Inflammatory functional iron deficiency anemia is a common clinical feature in hemodialysis populations. This condition represents an inefficiency of erythropoiesis, as evident by the need for elevated and escalating doses of ESAs or parenteral iron (or both), in order to maintain serum hemoglobin at an acceptable value. These high doses of ESAs and the maintenance of a high ferritin level are associated with increased risk of cardiovascular complications, the former of which is highlighted by the Agency's boxed warning on ESA product labeling advising conservative serum hemoglobin targets and avoidance of continued ESA dose escalation in hyporesponsive patients.

Despite the fact that the concept of inflammatory risk in renal patients has been in the public domain for decades, with an active basic research and clinical investigational community focused on its remediation, no therapy has been specifically designed or developed to address it. The advancement of an anti-inflammatory therapy which improve iron utilization and ultimately reduces the need for escalating doses of ESAs and / or parenteral iron would be a paradigm shift in the care of these patients.

As for the risks associated with administration of COR-001, nonclinical toxicology studies (See [Investigator's Brochure](#)) established the no-observed adverse effect level by the maximal dose administered. Both in terms of local and systemic effects, COR-001 was well tolerated, with no apparent adverse findings. Of note, the highest COR-001 dose planned for study allows an over 20-fold margin to NOAEL in the non-clinical toxicology program.

In Study D4430C00001 (AstraZeneca IND 114,712), COR-001 was well-tolerated in the three patients who received a single 30 mg dose. No patients died, no patients reported SAEs, and no patients discontinued the investigational product or from the study due to an AE. All AEs were considered to be mild to moderate in intensity. Overall, the most commonly reported AE was vomiting followed by diarrhea, reported by patients on COR-001 only. Although high and low laboratory values were reported for all 4 patients, no specific trends could be observed, with the exception of changes in the WBC and neutrophil counts. No other notable changes in laboratory parameters (including liver function), vital signs, or physical assessments as related to safety were noted.

Available data for anti-IL6R (tocilizumab) and anti-IL6 (siltuximab) therapies suggest neutralization of IL-6 have acceptable safety and tolerability profiles for the indications studied. Infusion-related and life-threatening hypersensitivity reactions are rare with these agents. Anti-inflammatory therapies in general run the risk of inducing immune suppression and promoting the emergence of infections, sometimes serious in nature. Although anti-IL-6 therapies lower neutrophil counts and may induce frank neutropenia, their rates of infectious complications appear to be similar to other immune-modulatory biologic agents when accounting for patient-specific factors ([Sakai 2015](#), [Sanofi 2016](#)). Gastrointestinal perforation has been associated with anti-IL-6 therapy, however data suggests proper exclusion criteria may mitigate these risks ([Tanaka 2014](#)).

The inclusion and exclusion criteria and monitoring schema employed in the planned clinical studies are designed to minimize and manage the potential risks of COR-001 therapy as inferred from other anti-IL-6 therapies. The exclusion of patients with known infection, the use of absolute-neutrophil count stopping rules, prohibition of the use of live vaccines and certain concomitant medications which are metabolized by the CYP system and display narrow therapeutic windows, exclusion of patients with a history of diverticulosis, as well as the use of the CTCAE system of adverse event reporting and maximum tolerated dose definition are designed to minimize the drug-associated risks to study patients.

COR-001 will be administered in a monitored setting (the hemodialysis unit) where frequent laboratory measurements (to ascertain for effects such as altered liver function and elevation in serum cholesterol) and close contact with dialysis staff will allow for prudent monitoring and early treatment of complications should they occur.

Finally, the use of a mechanistically-derived genotype patient selection strategy is intended to enrich the enrolled cohort for patients with the greatest likelihood of response to anti-IL-6 therapy. Therefore, the treatment is precisely targeted to the population who might benefit the most.

On balance then, the Sponsor proposes the potential risks to patients in this study are justifiable and the benefit-to-risk ratio positive. Patients will be consented as to the potential risks and will be required to sign an ICF documenting their understanding of these risks and willingness to participate in the study.

4 SELECTION OF STUDY POPULATION AND CRITERIA FOR WITHDRAWAL

4.1 Inclusion Criteria

To be eligible, potential study patients must meet all of the following criteria:

1. Age \geq 18 years at the time of signing of the ICF.
2. Receiving chronic hemodialysis for at least three (3) months prior to Screening via an arteriovenous fistula or arteriovenous graft.

Note: Every effort will be made to recruit patients who have a well- functioning arteriovenous fistula or graft to minimize the chance of requiring a central venous catheter during the Treatment Period.

3. The patient agrees to comply with the contraception and reproduction restrictions of the study:

Women of childbearing potential must be using a method of contraception, that is “highly effective” (i.e., $<$ 1% failure rate, see [Appendix F](#))

OR

Postmenopausal women must have had no menstrual bleeding for at least 1 year before initial dosing and either be over the age of 60 years or have an elevated plasma follicle-stimulating hormone (FSH) level (i.e., $>$ 40 mIU/mL) at Screening;

AND

All female patients of childbearing potential must have a documented negative pregnancy test result at Screening. Patients with elevated β -HCG levels believed to be due to end-stage renal disease may be enrolled if documented to not be pregnant.

4. The patient is able to give written informed consent and has signed a consent form approved by the Investigator's Institutional Review Board (IRB) or Independent Ethics Committee (IEC).
5. At least one documented $\text{spKt/V} > 1.2$ within 8 weeks prior to the Full Screening Period.
6. “Genotype positive” (genotype GG or AG, as defined by the Central Lab via genetic testing developed by the Sponsor) at Screening.
7. Two serum IL-6 levels \geq 4 pg/mL measured at least 1 week apart during the Screening Period.

8. Receiving one of the following IV or SC ESA drugs continuously prescribed for a minimum of 8 weeks prior to Full Screening: epoetin alfa, darbepoetin alfa, or methoxypolyethylene glycol-epoetin beta.
 - Epoetin alfa must not have had more than one dose missed or held during Week -3 weeks prior to Randomization.
 - Darbepoetin alfa must not have had any doses missed or held during the 4 weeks prior to Randomization.
 - Methoxypolyethylene glycol-epoetin beta must not have had any doses missed or held during the 6 weeks prior to Randomization.

9. Stable ESA doses prior to randomization, defined as follows:
 - For ESAs dosed weekly or more frequently:***
No change in the total weekly dose during Week -1 compared with Week -2.
 - For ESAs dosed less often than weekly:***
Any dose given during Full Screening Week -2 and Week -1 is unchanged from the immediately preceding dose.
 - Note: If a dose was given on both Week -2 and Week -1, then both doses are the same. (These 2 doses may be different than earlier doses).

10. Has been receiving intravenous (IV) or dialysate iron regularly and continuously (e.g., with each dialysis or each week) during the 3 weeks prior to randomization OR has received no IV or dialysate iron during this time frame and use of IV or dialysate iron is not anticipated through Study Week 24.
 - If parenteral iron has been administered during the 3 weeks prior to randomization, the regimen has been stable (same elemental iron dose, same frequency, and same iron product) with no more than 2 missed or held doses if dosed with each dialysis and no missed or held doses (if dosed weekly or less frequently) during this time frame.

11. If receiving oral ferric citrate, the patient has been prescribed it for at least 2 weeks prior to Full Screening and the dose is not anticipated to be changed through Study Week 24.

12. At least 2 ferritin values during Screening > 300 ng/mL.

13. At least 2 TSAT values during Screening between 15% and 50% (inclusive).

14. ESA resistance index (confirmed by the Sponsor) during the 2 weeks prior to randomization:

For patient receiving epoetin alfa:

$$\frac{\text{Total weekly dose of epoetin alfa (units)}}{(\text{hemoglobin [g/dL]} * \text{target dry body weight [kg]})} > 8 \text{ units/kg per g/dL}$$

For patients receiving darbepoetin alfa:

$$\frac{\text{Total weekly dose of darbepoetin alfa (mcg) * 300}}{(\text{hemoglobin [g/dL]} * \text{target [kg]})} > 8 \text{ units/kg per g/dL}$$

For patients receiving methoxy polyethylene glycol-epoetin beta:

$$\frac{\text{Weekly dose of methoxy polyethylene glycol-epoetin beta (mcg) * 300}}{(\text{hemoglobin [g/dL]} * \text{target dry body weight [kg]})} > 8 \text{ units/kg per g/dL}$$

If the ESA is dosed less often than once a week, divide the dose by the dosing interval to determine the weekly dose. For example, Weekly dose = dose given every two weeks ÷ 2.

The first day of each week used for calculations is defined as the first dialysis day of the Week (i.e., Monday or Tuesday).

15. During the 4 weeks prior to randomization, the mean of 3 consecutive hemoglobins between ≥ 8.5 and ≤ 11.0 g/dL, with the difference between the first and last measurements being < 1.2 g/dL.

Note: Qualifying hemoglobins must be drawn 2 or more days apart pre-dialysis, with no more than 2 measurements within a calendar week. There must be at least 9 days between the first and last of the 3 qualifying hemoglobin values.

16. Investigator anticipates no change to ESA, parenteral, or oral iron products, doses, or dosing regimen during Study Weeks 1 through 4 and that following the protocol guidance for ESA and iron dose changes ([Appendix C](#)) will be clinically appropriate for the patient.

17. Serum Vitamin B-12 and folate levels above the laboratory lower normal range during Full Screening.

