3 INVESTIGATIONAL PLAN

3.1 Overall Study Design and Plan: Description

This is a randomized, double-blind, placebo-controlled trial designed to evaluate the safety, pharmacokinetics, and pharmacodynamic effects of multiple doses of COR-001 or placebo administered to sequential cohorts of hemodialysis patients.

Ten hemodialysis patients will be randomized to COR-001 or placebo within each dosing cohort. When a higher dose than studied in a prior cohort is being initiated, the first 2 (sentinel) patients in that cohort will be randomized 1:1 to COR-001 or placebo; the remaining patients will be randomized at least 48 hours later in a 7:1 ratio of COR-001 to placebo.

Prior to dose escalation (i.e., higher total dose than studied in the preceding cohorts), there will be a formal safety review by the Safety Review Committee (SRC), which will include at least one nephrologist. The SRC will specifically determine whether the maximum tolerated dose (MTD) has been exceeded based on protocol-defined dose-limiting toxicities occurring through Study Day 21 in the 8 actively-treated patients in the current cohort (see [Figure 2](#)). In addition, PK and PD results will be reviewed to assess the appropriateness of the next planned dose and to guide revision of the next dose to be evaluated, if necessary. The planned doses are shown in [Table 2](#). These doses may be adjusted based on accruing data; however, the maximum dose to be studied will not exceed the planned total dose in Cohort 4 (60 mg every 14 days [6 doses]).

A single interim analysis (described in [Section 11.5](#)) is planned to enable future program planning.

Patients will undergo a Screening Period during which the ESA dose and parenteral iron doses must have been stable, as defined in the inclusion and exclusion criteria. Patients randomized to both COR-001 and placebo will be continued on ESA and parenteral iron (if being given).

Patients meeting the entry criteria will be randomized on Day 1 (a dialysis day), following which they will receive the first dose of Study Drug during dialysis. Additional visits will follow the schedule of events ([Appendix A](#)). All subsequent Study Drug infusions will also be administered during dialysis and study visits will coincide with regularly scheduled dialysis treatments. Patients dropping out (i.e., prematurely discontinuing Study Drug treatment) for reasons unrelated to safety may be replaced.

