3.4 Duration of the Study

The total study duration for an individual patient will be approximately 9 months, excluding the Screening Period. The study periods are as follows:

- Initial Screening Period: Up to 2 weeks [Days -28 to -15]
 - Starts with the first date that Initial Screening procedures were performed. The first procedure also defines the Initial Screening visit date.
- Full Screening Period: up to 2 weeks [Days -14 through Day -1]
 - Starts with the date of the Week -2 Visit

- Treatment Period: 12 weeks [Week 1, Day 1 through Week 12]
 - Safety Follow-Up Period: 12 weeks [Weeks 13 through 24]
- Extended Follow-Up Period: 10 weeks [Weeks 25 through 35]

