6. ERYTHROPOIESIS-STIMULATING AGENTS AND PARENTERAL IRON DOSES

ESA dosing will be summarized separately for EPOGEN (epoetin alfa), ARANESP (darbepoetin alfa) and MIRCERA (methoxy polyethylene glycol-epoetin beta) respectively. Historic ESA doses prior to randomization will be summarized weekly by treatment group for the pharmacodynamic analysis population. The mean weekly dose from Week -10 through Week -1 will also be computed for all ESAs. Percent change from baseline in ESA dose, change in ESA dose with ESA normalized to EPOGEN units, and change in ESA to a threshold value will also be computed with all ESAs pooled.

The following analyses will be performed:

- Comparison of the mean weekly ESA dose expressed in EPOGEN units prior to randomization to the post-randomization mean weekly dose for each 4-week interval in the Treatment and Safety Follow-up periods (e.g. Weeks 1-4, 5-8, etc). Inferential statistics will be performed for the Week 8-12 and the Week 1-4 periods.
 - Conversion of MIRCERA and ARANESP doses to EPOGEN units will be as follows:

$$\text{MIRCERA or ARANESP dose in mcg} * 300 = \text{EPOGEN unit equivalent dose}$$

- The percentage change from baseline with all 3 ESAs combined will be calculated for each 4-week interval in the Treatment and Safety Follow-up periods (e.g. Weeks 1-4, 5-8, etc). Inferential statistics will be performed for the Week 8-12 and the Week 1-4 periods.
- The number and percentage of subjects with dose change by +/- $\geq 25\%$, +/- $\geq 50\%$, and +/- $\geq 100\%$ will be computed for each 4-week interval in the Treatment and Safety Follow-up periods (e.g. Weeks 1-4, 5-8, etc).

Calculation of the Baseline ESA Dose

The baseline dose will be the baseline mean weekly dose for each ESA as defined below multiplied by 4.

- For EPOGEN, the baseline will be the mean weekly dose based on the 2 weeks immediately prior to randomization multiplied by 4.

- For ARANESP and MIRCERA, the baseline will be the mean weekly dose based on the 2 doses immediately prior to randomization multiplied by 4.
- The baseline dose will be normalized as the average dose per week during the time period of the doses used to define the baseline multiplied by 4.

Calculation of the Post-Baseline ESA Dose

- The post-baseline dose will be calculated based on the sum of all doses during a given time interval and will be expressed as the average dose per week during that time period multiplied by 4 or the number of weeks in the interval.

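### Criterion #9 tests no dose when a long-interval ESA has none in Weeks -2 and -1, and the SAP's two-dose ESA baseline can then mix the old and new dose

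*Protocol*

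**What the plan says.** Protocol Section 3.1 sets the intent: "Patients will undergo a Screening Period during which the ESA dose and parenteral iron doses must have been stable". Criterion #9 defines stability. For ESAs dosed less often than weekly it requires that "Any dose given during Full Screening Week -2 and Week -1 is unchanged from the immediately preceding dose". A Note adds that if both weeks contain a dose the two must be equal, and that "These 2 doses may be different than earlier doses".

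Criterion #8 deals with missed or held doses, for example "Darbepoetin alfa must not have had any doses missed or held during the 4 weeks prior to Randomization". It does not deal with changes in dose size. For epoetin, Section 4.1 reads "Epoetin alfa must not have had more than one dose missed or held during Week -3 weeks prior to Randomization"; the synopsis words the same limit differently, as Week -3 prior to randomization.

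For ARANESP and MIRCERA, SAP Section 6 states that "the baseline will be the mean weekly dose based on the 2 doses immediately prior to randomization multiplied by 4". SAP Section 2.5.1 compares the Weeks 1-4 total with the same two-dose mean. SAP Section 6 plans inferential statistics on ESA dose for Weeks 1-4 and Weeks 8-12.

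**The concern.** Criterion #9 is conditional on a dose falling in a 14-day window. Someone dosed every 3 or 4 weeks may have no dose there, and the condition is then met automatically. A dose changed in Week -3 or Week -4, still inside Screening, counts as stable.

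The SAP baseline has no such window. It takes the last two doses whenever they were given, so for this patient it averages the dose before the change with the dose after it. A patient whose dose never moves after randomization then appears to have changed dose in an inferential ESA comparison. The same patient can appear in the SAP 2.5.1 list of dose adjustments, which gives no tolerance. If that list is what SAP 7.5 means by off-protocol dosing, the patient is also removed from the anemia sensitivity analyses.

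**Working it through.** The plan states no figure on this point, so there is none to reproduce.

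**Step 1. Does another rule close the gap?**

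- #8 limits missed and held doses, not changed ones.
- #16 looks forward to Weeks 1-4.
- #15 limits hemoglobin drift and does not look at ESA dose.
- The Schedule of Events says to keep ESA doses stable in Screening, but its footnote defines stability as #8 and #9.
- Section 5.2 has sites watch ESA stability during Initial Screening under that schedule, with investigator judgment.

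None of these compares the last dose with the one before it.

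**Step 2. When is no dose tested?** Assume dosing on schedule at an interval of I days, with the last dose before randomization equally likely on any of Days -1 to -I. The share with no dose in Days -14 to -1 is max(0, I - 14)/I.

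| Interval | Share with no dose tested |
|---|---|
| Every 2 weeks | 0/14 = 0% |
| Every 3 weeks | 7/21 = 33% |
| Every 4 weeks | 14/28 = 50% |

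If one dose falls in the window it must equal its predecessor. If two do, the Note makes them equal. In both cases the last two doses match and the SAP baseline is clean, so the defect is confined to the no-dose case.

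**Step 3. What does the SAP baseline then show?** Take every-4-week dosing, an old dose of 1, a new dose of r, and no change after randomization. Two doses cover 8 weeks.

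- Baseline = [(1 + r)/8] × 4 = (1 + r)/2
- Weeks 1-4 dose = r
- Apparent change = 2r/(1 + r) - 1

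| New/old dose (r) | Apparent change, Weeks 1-4 |
|---|---|
| 0.50 | -33.3% |
| 0.75 | -14.3% |
| 1.00 | 0% |
| 1.25 | +11.1% |
| 1.50 | +20.0% |
| 2.00 | +33.3% |

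The 25% step is an illustration; Appendix C gives it only for on-study increases in Weeks 5-24. In EPOGEN units, a rise from 100 to 125 mcg gives a baseline of (225/8) × 4 × 300 = 33,750 and a Weeks 1-4 dose of 125 × 300 = 37,500, a difference of 3,750. The artefact reaches the SAP's 25% change category only for r of at least 5/3 (a 67% rise) or at most 0.6 (a 40% cut).

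**Step 4. Other intervals and windows.** The SAP sums the doses actually given, so the count of doses in the window matters.

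- Every 3 weeks, Weeks 1-4: the baseline for a constant dose is (2/6) × 4 = 1.333. One dose in the window reads -25% and two read +50%. With a 25% rise the baseline is (2.25/6) × 4 = 1.5, and the readings are 1.25/1.5 - 1 = -16.7% or 2.5/1.5 - 1 = +66.7%.
- Every 4 weeks, Weeks 8-12 (five weeks), using the multiply-by-4 convention: with a 25% rise, one dose gives (1.25/5) × 4 = 1.0 against 1.125, or -11.1%. Two doses give 2.0 against 1.125, or +77.8%.

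The straddling multiplies each reading by the same 1.25/1.125 = 1.111, but the percentage seen is +11.1% only for every-4-week dosing in Weeks 1-4.

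**Step 5. Effect on a group mean.** Up to six cohorts with two placebo patients each give about 12. One affected placebo patient with a 25% rise moves the placebo mean percent change by 11.1/12 = 0.9 percentage points.

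**Step 6. Epoetin, as a secondary case.** #9 compares only Week -1 with Week -2, and the SAP baseline is those two weeks. If one of three weekly doses is held in each, the baseline is 2/3 of the regimen. Full dosing afterwards then reads as 1/(2/3) - 1 = +50%.

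**The case against.** The strongest reply is that this is rare and neutral between arms. It needs an interval longer than 2 weeks, no dose in the last 14 days, and a recent dose change, all in one patient. The documents give no frequency for any of these. The change precedes randomization, so it cannot favour an arm in expectation. Both points stand.

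Several stronger readings are tempting, but the documents do not support them.

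- A reader might infer that the ERI endpoints are distorted. SAP 7.2 defines the Screening ERI as the qualifying ERI under #14, which divides dose by interval. The two-dose mean does not enter it.
- A reader might take the Note as contradicting the rule. The Amendment 2 summary of changes presents it as a clarification for patients dosed in both weeks, and there the last two doses are equal. It still needs reconciling, because the main rule ties a Week -2 dose to its predecessor and the Note lets it differ.
- A reader might call the epoetin allowance an oversight. Amendment 2 gives a reason: holds that leave the total weekly dose unchanged are acceptable. What remains is only their effect on the SAP baseline.

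It can also be said that SAP 2.5.1 and 7.5 already separate such patients. That is partly true, but the flag would label them as having changed dose after randomization. SAP 7.5 also does not say outright whether the 2.5.1 list or the dosing guidelines repeated beneath it define off-protocol dosing.

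Finally, counting doses in fixed windows creates larger swings than the artefact does (Step 4). That stands, and the fix below does not remove it.

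**Conclusion.** The point holds within limits. On the text, #9 is empty for a long-interval ESA with no dose in Weeks -2 and -1, and the SAP baseline then averages across any dose change just made. For every-4-week dosing held constant after randomization, Weeks 1-4 misstate the ESA change by +11.1%, +20.0% or -14.3% for a prior rise of 25%, a rise of 50% or a cut of 25%. The 33% and 50% shares with no dose tested rest on evenly spread dosing dates, which is an assumption.

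The reach is the ESA-dose analyses in SAP 6 and the flags in SAP 2.5.1 and 7.5. A reader might infer that a few such patients would bias the treatment contrast. The documents do not support that: the number affected is not given, the error is noise in expectation, and one placebo patient in 12 shifts the mean by about 0.9 points.

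**What to change.** In SAP Sections 6 and 2.5.1, add that when the last two ARANESP or MIRCERA doses before randomization differ, the baseline weekly dose is the last dose divided by its dosing interval, then multiplied by 4 as now. In the every-4-week case the baseline becomes r and the false Weeks 1-4 change becomes 0%. List these patients separately in the SAP 7.5 sensitivity analysis. As a secondary item, also list epoetin patients with doses held in both Week -2 and Week -1.

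Separately, the sponsor should reconcile criterion #9, its Note, the two wordings of #8 (synopsis and Section 4.1) and the SAP baseline so that all refer to the same doses. No particular missed-dose or dosing rule is proposed here.

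The cost is a few lines of SAP text. SAP 6 already summarises ESA history from Week -10, so no new data are needed, and dose over interval is already the method in #14. Any change to eligibility wording would affect only patients still to be enrolled; Amendment 3 already records the Cohort 5 dose and the SAP's database locks end with Cohort 6, so its remaining use may be small.
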